## **6 Risks and benefits of the device and clinical investigation**

### **6.1 Anticipated clinical benefits**

Patients participating in this study will follow routine cochlear implantation and treatment. Electrode position will be measured making use of CT scans routinely performed during CI treatment. There is no anticipated clinical benefit for the patients through participation in the clinical investigation.

However, understanding the specificity of the candidate algorithm, and characterisation of the measures in the clinical setting, is expected to benefit cochlear implant patients in the future through a more consistent positioning of the electrode array. Additionally, it is possible that the use of such algorithms will in future eliminate the need for post-operative imaging and so benefit implanted patients through reduced exposure to radiation.

### **6.2 Anticipated adverse device effects**

The potential adverse device effects while using the components listed in section 4 to generate electrical stimulation of the cochlea during surgery and during the routine visits after surgery are no greater than that posed through the clinical routine via NRT, facial nerve monitoring, etc. All devices used in this clinical investigation are CE marked and TGA approved.

The study participants will undergo a standard cochlear implantation surgery, and are therefore identical to the risks in cochlear implant surgery as described by the package insert. No feedback on analysis of the intra-operative measurements will be provided to the surgeon during the operation.

The trans-impedance and Auto NRT measurements will be performed with the CSEP software and therefore be subject to the standard adverse events associated with the use of this software. The measurements will be performed by expert clinicians trained on the use of this software in normal clinical practice. The risks of participating in this study are therefore identical to the risks in normal clinical care.

The candidate algorithm is run on the data by an independent party at specified intervals on the data collected by the above-mentioned components. The person who performs the analysis does so in de-identified data after study closure. The algorithm evaluation will be conducted on the bench without any patient involvement. Thus, there are no anticipated adverse events resulting from the use of the algorithm.

### **6.3 Residual risks related to the device**

The residual risks (e.g. overstimulation) including instructions for mitigation are listed in the labelling and investigators are instructed to follow these.

## 6.4 Risks associated with participation in the clinical investigation

Participants in the clinical investigation are exposed to the risks associated with standard cochlear implant surgery, general anaesthesia, and NRT measures as well as CT scans before and after surgery within the routine clinical procedures. The trans-impedance and voltage measurement being an interventional measurement prolongs the surgery by 1 minute. This will always happen in consultation with the surgeon and the anaesthetist and may even be conducted during the wake up phase after anaesthesia not to put the patient at an additional risk.

Interactions with concomitant medical treatments are not envisaged during the clinical investigation. Please see the labelling associated with the components used in this study.

## 6.5 Risk mitigation

This study will follow routine clinical practice and risk mitigation.

As precaution to avoid any risks associated with data protection the patient's identity and all information collected during the investigation will be kept strictly confidential and in accordance with EU and Australian data protection laws. Each participant's data will be given a unique code and the list of codes will be kept by the investigator as described in the data privacy section.

No other risks are expected that would exceed the clinical routine practice of CI implantation and clinical follow-up.

The risk of electrode position determination by an experimental telemetry processing algorithm is mitigated by executing the algorithm on the exported data completely independent of clinical procedures and by keeping the outcomes of these algorithms blind to the investigators until the study is officially closed. The patient management is not dependent on the findings from this study.

## 6.6 Risk-to-benefit rationale

The risks associated with this study will be kept to a minimum. The study population consists of conventional CI candidates, scheduled for CI treatment. Besides the trans-impedance and intra-cochlear voltage measurements, the study will capture data that are collected during routine clinical practice. The trans-impedance and intra-cochlear voltage measurements will be collected with the CE marked and TGA approved CSEP application. Collection of this data takes less than 1 minute per session in addition to the clinical routine measures and does not create any additional risks beyond a slight prolongation of the surgical procedure with the measurement time (only for the intra-operative measurement session).

The benefit-risk profile for this study is considered positive given the low risks and the potential for future improvement of CI treatment including access to a non-invasive measurement of electrode array positioning and thereby minimization radiation exposure through radiological imaging currently routinely used for detection of electrode position.

## 7 Objectives and hypothesis

Primary objective(s):	To explore the specificity (the number of true negative responses divided by the number of negative (non-anomalous) cases) of a candidate algorithm that has the ability to detect low incidence deviations from a normal electrode position using trans-impedance measurements
-----------------------	---

Secondary objective(s):	
 
1. To explore the association between the trans-impedance and intra-cochlear voltage measurements, NRT thresholds and the intra-cochlear electrode array position.
 
2. To investigate changes in the trans-impedance and intra-cochlear voltages along with NRT thresholds over time to identify the stability of the measurements.
 
3. To establish a database of trans-impedance and intra-cochlear voltages, NRT thresholds and CT/DVT images for educational, research and development purposes.
 

Primary endpoint:	Trans-impedance and intra-cochlear voltage measurements for each electrode contact after electrode insertion with post-operative CT/DVT Scan.
Secondary endpoints:	
 
1. NRT thresholds for each electrode contact during surgery and pre-operative CT/DVT Scan co-registered with the post-operative CT/DVT Scan collected for the primary endpoint.
 
2. Trans-impedance and intra-cochlear voltage measurements and NRT thresholds for each electrode contact at first activation and 3 months post-operative
 
3. Validated database entry of trans-impedance and intra-cochlear voltage measurement and NRT thresholds during surgery, at first activation and three months post-operative as well as the pre-operative and post-operative CT/DVT Scans respectively.
 

Hypothesis	
H0: The specificity of an algorithm that will detect low incidence deviations from a normal intra-cochlear electrode insertion will be < 98%.
 
H1: The specificity of an algorithm that will detect low incidence deviations from a normal intra-cochlear electrode insertion will be ≥ 98%.

## 8 Design of the clinical investigation

### 8.1 General

The current clinical investigation is designed as descriptive research with sequential enrolment. The treatment schedule is according to the clinical routine visit schedule by prospectively adding a one minute trans-impedance and voltage measurement to the clinical routine measurements. The purpose of the clinical investigation is to collect and describe the characteristics of the trans-impedance and voltage measurements to explore the specificity of a candidate algorithm that has been developed to detect certain anomalous electrode array positions. Insertions will be classified based on the electrode position in relation to the cochlea structures as determined from pre- and post-operative CT scans. The classification will establish an insertion as either normal or showing one or more anomalous properties. The study will then provide the candidate algorithm with the 154 classified insertions to explore the specificity of the algorithm, this should allow a specificity of up to 98% to be established with a 90% confidence. The trans-impedance and voltage measurements are obtained at repeated visits to evaluate the candidate algorithm specificity over time.

 Assuming up to 9 anomalous insertions in the sample of 154 implantations.

Blinding procedures are not appropriate for the voltage and trans-impedance measures to be collected with the clinical routine software CSEP, as it is not possible to conceal the presence, or absence, of the devices from the investigators.

Since the candidate algorithm to detect certain anomalous electrode array positions has not been implemented in any CE marked and TGA approved software, no real time feedback on any insertion related events will be provided to the clinician nor surgeon throughout the surgery nor aftercare. The surgeon and the clinician shall not deviate from their established clinical routine measures as CT imaging, x-ray or objective measures to detect anomalous electrode array positions and are advised not to interpret the voltage and trans-impedance measures.

In addition, the data will be analysed to establish the normative range of trans-impedance and voltage measurements in CI532 and CI512 electrode arrays, the correlation to NRT measurement, to correlation to electrode-to-modiolus distance (from CT/DVT Scans) and the normal variations of those measures over time.

The CT/DVT imaging before and after surgery and the CSEP measurements during and after surgery is part of the clinical routine in CI treatment and patients will be selected who follow this clinical routine.

In addition, the measurements, CT/DVT scans and classifications will be de-identified and stored in a database to support the further development and validation of algorithms. Those insertions showing the presence of anomalous properties will be excluded from the dataset that is presented to the candidate algorithm but will be included in this database. To allow for the exclusion of these insertions an additional 9 subjects are added to the study.

Depending on the recommended practice in the clinics the measures of surgeries performed by experienced and unexperienced surgeons will be collected. For retracement the name of the inserting surgeon is labelled on the surgical questionnaire.

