## 5 Justification for the design of the clinical investigation

Several researchers have demonstrated the utility of trans-impedance matrix and other voltage measurements (Hey et al. 2015, Vanpoucke et al. 2004, Vanpoucke et al. 2012) to identify the intra-cochlear electrode positioning. The current investigation is designed to both evaluate a candidate algorithm for detecting the occurrence of gross anomalies in position (e.g. tip fold-over or the electrode array not in the cochlea) and to provide a robust dataset in a clinically representative sample of cochlear implant recipients that can be used to test the specificity and sensitivity of future electrode position feedback algorithms. Such algorithms have potential clinical application in providing objective feedback to the surgeon at the time of electrode insertion to inform the surgeon on electrode placement without additional radiological imaging, and may in future lead to improved clinical outcomes for cochlear implant recipients.

No large database of combined high quality imaging of the intra-cochlear electrode position and reliable trans-impedance measurements exist. It is only relatively recently that it has become possible to determine accurate intra-cochlear electrode position, as a result of advances in scanner technology. Also, the trans-impedance measurements (contained in Custom Sound™ Electro Physiology) that will be used in the study only recently became available. Earlier versions of this tool did not provide sufficient resolution to accurately measure the electrical spread curves.

To explore the decision algorithm, a large dataset is needed. This study will systematically collect a large pool of trans-impedance measurements of CI recipients combined with state of the art imaging of the implanted electrode as part of the clinical routine. Image analysis will allow an expert radiologist/ENT surgeon to determine for each implantation whether it is a normal case or not. The trans-impedance measurements will be analysed by the decision algorithm, and the agreement with the human experts will be established. This exploration of the specificity of the candidate algorithm is the main target of this study, thus being evaluated on the bench without patient involvement.

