### 8.4.2 Surgery

After electrode array insertion, the extra-cochlear electrode lead is placed and the plate electrode is covered by skin flap. The NRT, trans-impedance and voltage measurements are performed using CSEP. The CSEP measurements take approximately 11 minutes for Auto-NRT with conditioning on 22 electrodes and 1 minute for trans-impedance and voltage measurements. Since Auto-NRT is part of the clinical routine, the additional time effort for this study is 1 minute.

The following sequence applies:

1. Auto NRT with conditioning on 22 electrodes
2. Trans-impedance and voltage measurements

The CT/DVT scan of the intra-cochlear electrode array positioning will be conducted as part of the clinical routine battery.

Within the surgical questionnaire the number of surgeries of the implanting surgeon, insertion related events as well as the corrective actions (if applicable) are documented. This information will be entered into the corresponding CRF after review by the surgeon.

In case the electrode array placement needs to be corrected as part of the clinical and surgical routine, the following workflow maintains:

1. If not already done as described before: Run the trans-impedance and voltage measurements before removing the electrode array.
2. Correct the electrode array placement as per normal clinical routine.
3. After successful reinsertion / corrective action of the position of the electrode array, run the Auto-NRT, trans-impedance and voltage measurements again.

The intra-operative measures with CSEP will be exported as cdx/csv files and transferred in an anonymized form to Cochlear.

An active follow-up on the occurrence of (S)AE, ADE, DD applies. Protocol Deviations (if applicable) will be documented as soon as possible after occurrence.

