## 9 Statistical Considerations

### 9.1 Sample Size Calculation

An in-depth description of the statistical characterisation and correlation will be part of the Statistical Analysis Plan. Final statistical analysis will be conducted on a clean and complete database after database closure.

The candidate algorithm provides the ability to detect gross electrode position anomalies (eg. tip fold-over or electrode not in the cochlea). It provides binary outputs; a value of zero (negative result) or a value of one (positive result). A value of zero indicates that the algorithm concluded that an anomalous position has not occurred and the value of one indicates that the algorithm concluded that an anomalous position has occurred. To be useful as a tool that can replace routine use of X-rays and CT scans, the algorithm is required to have a minimal false positive rate. To ensure that this expectation is reasonably fulfilled, the 98% specificity target is set to be the lower bound of the 90% binomial confidence interval for the specificity of the algorithm. An iterative approach was adopted to estimate the required patient sample size which takes into account the likelihood of anomalous position events. It was assumed that the occurrence of a tip fold-over (the principal form of position anomaly under consideration) follows a binomial distribution with a positive probability of around 4% based on the weighted average percentage for tip fold-overs in pre-curved arrays reported by Grolman et al. 2009 and Zuniga et al. 2016. Using the Clopper-Pearson method a sample size of 154 was selected, which gives an 89% chance of 9 or less tip fold-overs taking place, resulting in at least 145 'normal' insertions. If the algorithm correctly diagnoses all 145 insertions, the lower bound of the two-tailed 90% confidence interval for specificity will be 97.97% which is approximately 98%. In other words, if the algorithm correctly identifies all 145 cases as 'normal' then it can be concluded that its specificity is 98% or better with 90% confidence.

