### 9.2 Candidate algorithm exploration

To explore the specificity of the candidate algorithm it will be provided with the trans-impedance data collected at surgery, first activation and 3 months post-operatively for insertions that has been determined not to contain any anomalous electrode array position based on the CT Scans.

In each instance the result of the algorithm will be analysed to determine the specificity based on the amount of positive and negative results returned by the algorithm.

---

 For the sample size calculation, it is assumed that the sensitivity (true positive) of the candidate algorithm is 90%.

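### Protocol 8.1 contradicts itself on which insertions the algorithm is given; the normal-only route tells the runner the right answer, with no masking or threshold lock, and leaves the recorded anomalies unused

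*Protocol*

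**What the plan says.** Protocol 8.1 first describes a run on everything: "The study will then provide the candidate algorithm with the 154 classified insertions to explore the specificity of the algorithm". The footnote to that sentence reads "Assuming up to 9 anomalous insertions in the sample of 154 implantations", so the 154 are understood to include anomalous cases. Further on, the same section says: "Those insertions showing the presence of anomalous properties will be excluded from the dataset that is presented to the candidate algorithm".

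The later text follows the second statement. Protocol 9.2 supplies recordings "for insertions that has been determined not to contain any anomalous electrode array position based on the CT Scans". Protocol 9.3 drops insertions with insertion-related events, SAP 3.1 step 1 names normal insertions, and SAP section 6 leaves out patients with a confirmed anomalous position. In SAP 3.1, however, the radiographic classification that defines a normal insertion is step 4, after the run (step 1), the collection of outputs and the count.

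Four other places bear on the choice:

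- Protocol section 5 promises that "the agreement with the human experts will be established".
- Protocol section 3 sets a positive predictive value of 60% as an aim of the current study. It also says that the tuning of the algorithm's threshold still has to be explored, and it puts sensitivity out of scope, to be studied in vitro.
- Protocol 8.4.2 secures a recording of a misplaced array when the surgeon corrects it: "Run the trans-impedance and voltage measurements before removing the electrode array".
- Protocol 6.2 has an independent party run the algorithm, and Protocol 6.5 keeps the outputs from the investigators until the study closes.

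**The concern.** An analyst cannot tell from these texts which dataset feeds the primary analysis, or whether the CT class is assigned before or after the run. The two routes differ in what the runner knows and in what the study can learn.

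If only CT-normal insertions are supplied, anyone who knows the plan knows that each output of 1 is an error. The stated masking runs the other way: investigators do not see the outputs. No text keeps the CT class from the runner, and no text fixes the algorithm version or threshold before the run. Knowledge of the truth combined with an adjustable threshold is how a specificity estimate becomes optimistic.

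The normal-only route also sets aside the cases that could show whether the algorithm detects anything in patients. On normals alone every flag is a false positive, so an observed positive predictive value would be 0 or undefined, and agreement with the experts can be checked in one class only.

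**Working it through.** **Inputs.** N = 154, n = 145, up to 9 anomalies and a two-sided 90% Clopper-Pearson interval (Protocol 9.1, SAP 2.1 and 2.2). Fold-over rate p = (5 + 4)/(0.48 × 303 + 72) = 0.04139 (SAP Appendix A). Assumed sensitivity 90% (footnote to Protocol 9.2; SAP 2.2).

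**The plan's own figures.**
- P(at most 9 fold-overs among 154) = 0.8925; the plan states 89%.
- Lower bound when all n are correct: 0.05^(1/n). For n = 145 this is 97.955%. The grid search in SAP Appendix A gives 97.975%; the plan states 97.97%.
- Positive predictive value = 0.0414 × 0.90 / (0.0414 × 0.90 + 0.9586 × 0.02) = 0.03726/0.05643 = 66.03%; the plan states 66.02%.

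All three reproduce, apart from rounding and the grid tolerance.

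**How close to the rule the study sits.** The literal rule in SAP 3.1 is a lower bound of at least 98%. That needs log(0.05)/log(0.98) = 148.3, so 149 of 149. P(at least 149 normals among 154) = P(at most 5 fold-overs) = 38%. At exactly 145/145 the literal rule is missed, and only the wording that asks for 100% of at least 145 is met.

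**How much one flag matters.** 144/145 gives a lower bound of 96.770%. The chance of 145/145 is 0.99^145 = 23% at a true specificity of 99%, and 0.995^145 = 48% at 99.5%. So a good algorithm will often produce a flag or two, and a threshold moved slightly to remove them would change the conclusion.

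**What goes unused.** Expected fold-overs: 154 × 0.04139 = 6.4. P(at least one) = 1 − (1 − 0.04139)^154 = 99.9%. Exact 90% intervals for detection in 6 cases:

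| Detected | 90% interval |
|---|---|
| 6/6 | 60.7% to 100% |
| 3/6 | 15.3% to 84.7% |
| 0/6 | 0% to 39.3% |

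**What the predictive value aim needs.** With specificity 98% and prevalence 4.14%, a value of 60% requires 0.0414 × s = 1.5 × 0.9586 × 0.02 = 0.02876, so s = 69.5%. A 0/6 result would contradict that, because its upper limit is 39.3%. A 6/6 result would be compatible with it but would not establish it, because its lower limit is 60.7%.

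**An algorithm that always outputs 0, on each route, with 9 anomalies.**
- Normal-only: specificity 145/145, lower bound 97.955%; nothing else is seen.
- All 154: specificity again 145/145, lower bound 97.955%. Detection is now seen to be 0/9 (upper limit 28.3%), and overall agreement is 145/154 = 94.2%.

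**The case against.** The strongest reply is that this is a declared exploratory, specificity-only study. Protocol section 3 says openly that sensitivity is out of scope, explains why, and assigns it to separate in vitro work. The all-154 sentence may be one loose phrase, since the exclusion is explicit later in the section and explains the 9 extra subjects; editing that one sentence would also remove the contradiction. The algorithm is run by an independent party on de-identified data after closure, and a fixed algorithm with binary output gives the same answers whatever the runner knows. The anomalous cases are not lost, because they stay in the database for later algorithms.

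Much of this stands. The scope limit is legitimate, and no powered sensitivity test is called for. It does not settle the order of steps in SAP 3.1, though, and independence does not mask a runner whose dataset contains one class. Protocol 6.2 also speaks both of specified intervals and of analysis after closure. The fixed-algorithm defence needs a lock that neither document states.

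Three stronger readings are tempting and are not supported:

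- **That the normal-only route is what lets a never-flagging algorithm succeed.** Anomalies are not in the denominator of specificity, so the result is the same on either route. The pass comes from the declared specificity-only rule.
- **That Protocol 9.1 rests replacement of imaging on false positives alone.** The sentence that opens "To be useful as a tool that can replace routine use of X-rays and CT scans, the algorithm is required to have a minimal false" asks for few false alarms, which is a necessary condition. Section 3 separately conditions useful feedback on adequate sensitivity.
- **That the in vitro study cannot answer the detection question.** Its protocol is not among the documents.

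**Conclusion.** The contradiction and the misplaced classification step are in current text and affect the primary analysis. The bias is a possibility, not a demonstrated fact: it depends on the threshold still being adjustable at the time of the run, which Protocol section 3 leaves open and nothing later closes. Where it operates, a single flag decides between lower bounds of 97.955% and 96.770%.

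The unused information is small but relevant. About 6 fold-overs are expected if the 4.139% rate holds and the cases are recorded. That is too few to estimate sensitivity well; the 3/6 interval overlaps both extremes. It is enough to make a complete failure of detection visible. Without these cases the 60% aim rests wholly on the assumed 90% sensitivity. The point is a low-cost improvement, not a must-fix.

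**What to change.** 1. Make Protocol 8.1, 9.2 and 9.3, SAP 3.1 and SAP section 6 describe one dataset, and put the CT classification and the run in a workable order.
2. State that the algorithm version and threshold are locked before the run, and record them.
3. Supply the recordings of all insertions, at each planned time point, as one coded batch without the CT class. Run once and freeze the outputs.
4. Then merge the class. Compute specificity in CT-normal insertions exactly as planned.
5. List the output for each confirmed fold-over or extra-cochlear array, with an exact 90% interval labelled descriptive. An array corrected during surgery may have a CT only of its final position (Protocol 8.2 allows the scan after surgery), so state the reference source for any pre-removal recording.
6. Say whether success means a lower bound of at least 98% or all of at least 145 correct; at exactly 145 the two disagree.

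Optionally, add to Protocol 9.1 that a low false positive rate is one requirement among others for replacing imaging.

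The cost is wording and one short table. N = 154 and n = 145 are unchanged, and no extra patients, scans or measurements are needed. The drawback is an imprecise detection figure that could be over-read, hence the descriptive label.
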